## **CHARACTERISTICS OF THE STUDY POPULATION**

### **1. Target Population**

Three hundred (150 HIV+ and 150 HIV-) adult male and female smokers 18 years of age or older who smoke at least 5 cigarettes per day and are interested in quitting smoking will complete the study. HIV-infected smokers will have been diagnosed with HIV/AIDS (identified through the UPENN CFAR Clinical Core, UPHS PennChart reviews and community-based HIV/AIDS organizations and events; see specific criteria below) and HIV-uninfected smokers will have no diagnosis of HIV, confirmed either via blood test (see recruitment strategy below) or self-report. Participants in the HIV+ and HIV- groups will be matched according to key demographic and smoking characteristics (see Accrual below).

At PENN, a previous nicotine patch trial recruited a sample comprised of 45% women and 16% racial/ethnic minorities (Schnoll et al., 2010b). A separate PENN smoking cessation trial that used targeted efforts to recruit minority smokers had a sample comprised of 55% women and 52% racial/ethnic minorities (Schnoll et al., 2011). The UPENN CFAR Clinical Core population is 78% African American and 4% Hispanic American.

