#### 2. Design

**Main Study.** This study will use a prospective observational matched-design to test whether HIV+ smokers (vs. HIV-smokers) are more likely to experience cognitive deficits during nicotine withdrawal and whether these deficits are predictive of smoking relapse. As shown in Figure 1, adult treatment-seeking smokers (N=300; 150 HIV+ and 150 HIV-) will complete this 12-week study, which is divided into two phases: a pre-quit laboratory phase (weeks 0-2) and a treatment phase (weeks 3-12). Subjects will complete two laboratory sessions during the pre-quit phase: once following 24 hours of mandatory smoking abstinence and once while smoking-as-usual (order counter-balanced; abstinence biochemically confirmed). A cognitive task battery assessing working memory, sustained attention, and response inhibition will be administered during each session. During the treatment phase, subjects will receive standard smoking cessation treatment, including six sessions of brief individual counseling (weeks 3-8) and eight weeks of open-label transdermal nicotine (TN) patch treatment (weeks 4-12) [34]. The primary outcomes will be: 1) cognitive performance (e.g., verbal and working memory) following 24-hours smoking abstinence (vs. smoking-as-usual) during the pre-quit phase, and 2) 7-day point-prevalence, biochemically confirmed abstinence rates at end-of-treatment (EOT) for the treatment phase. Since randomization is not possible in this study, we will rely on inclusion criteria and matching to reduce the potential for confounding. More specifically, participants will be

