**Figure 1. Study Time Points and Assessments**

matched on age, race, education, and smoking rate.

**Rhythm Monitoring Sub-Study.** This sub-study will explore differences in arrhythmia burden between HIV+ and HIV-smokers and will also look at the relationship between arrhythmic burden and cognitive function. Fifty smokers (25 HIV+ and 25 HIV-) will be asked to wear a non-invasive rhythm monitoring device for two 2-week periods during the course of the study: for two weeks prior to smoking cessation treatment (weeks 2-4) and then two weeks near the end of treatment (weeks 8-10).

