## 2. Statistical Analysis

### **Power Analysis and Sample Size.**

Our study is a longitudinal between-subject design that seeks to test the following hypotheses: 1) that HIV+ smokers experience larger abstinence-induced cognitive deficits than HIV- smokers (Aim 1); 2) have lower quit-rates than HIV-smokers following standard treatment (Aim 2); and 3) that the association between HIV status and relapse is mediated by abstinence-induced cognitive deficits (Aim 3). We have designed our study to achieve 80% power, testing at a global  $\alpha=0.05$  for each of the hypothesis families (Figure 1). Our sample size of 300 was determined primarily by Aim 2. Based on prior work, we expect a ~15% difference in abstinence rates between HIV+ and HIV- smokers (Ferketich et al., 2013; Humfleet et al., 2013; Matthews et al., 2013; Silagy et al., 2004). With 150 HIV+ vs. 150 HIV- smokers, we have 80% power to detect a difference of ~15 percentage points in point-prevalence abstinence (60% vs. 45%, 50% vs. 35%, 40% vs. 25%), using a z-test on log-odds with a type 1 error of 5%. For Aim 1, we will test the HIV status by abstinence condition (24-h abstinence vs. smoking-as-usual) interaction for 5 cognitive measures using a linear regression with one between- and one within-subjects factor. We will correct for 5 tests using  $\alpha=0.01$ . We have 80% power to detect medium effect sizes (Cohen's  $d=0.4$ ). For Aim 3, we will test whether abstinence-induced cognitive deficits predict quit rates and, using SEM, test whether cognitive deficits mediate the effect of HIV status on quitting. The primary aim will be to test the overall fraction of the effect mediated, which will be tested at  $\alpha=0.05$ , which gives 80% power to detect small to medium effects ( $d=0.32$ ). For our exploratory aim, the component individual deficits will be treated as secondary and tested individually as part of an exploratory analysis, also with a 5% type 1 error. To characterize cognitive deficits in HIV+ smokers, 150 subjects will give us an estimate for each measure with a 95% CI that is 0.32 standard deviations wide (Upper – Lower limits). We will estimate the within-subject correlation for these as repeated measures, with a 95% CI that is 0.32 wide (Upper – Lower) if  $r=0$ , 0.24 if  $r=0.5$ , and 0.14 if  $r=0.75$ . Power was calculated using PASS software, NCSS, Kaysville, UT.

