**Aim 1.** We will analyze neurocognitive data with multiple linear regression using a GLM framework. The outcomes will be cognitive deficits measured as a change in response values (see **Section D.4.d.** for description) due to abstinence challenge (24-h abstinence vs. smoking-as-usual). The hypothesized interaction effect of HIV+ status by abstinence condition will be tested by including dichotomous predictors, and examining the corresponding *z*-score. Although the groups will be matched on key variables, we may also include a small number of covariates (e.g., nicotine dependence, Shipley IQ) that show potential to control for error, admitted to the model at  $p=0.1$ . In conjunction with Aim 1, we will be estimating cognitive measures for the HIV+ group, within-subject correlations, and deficits that arise from abstinence challenge. We will summarize point estimates and provide 95% confidence intervals.

**Aim 2.** We will analyze point-prevalence quit rates using logistic regression. The hypothesized effect of HIV status (HIV+ vs. HIV-) will be tested by including a dichotomous term using the *z*-score. A small number of other potential controlling variables will be tested for inclusion ( $p=0.1$ ). Outcomes of the logistic regression analyses will be characterized by odds ratios (e.g., odds of quitting smoking) and 95% confidence intervals. Point-prevalence quit rates at EOT are the primary outcome. Secondarily, we will conduct logistic regression analyses for other assessments of quit rates, including prolonged and continuous abstinence.

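### The factors on which the HIV groups are matched are not guaranteed a place in the Aim 1 and Aim 2 models

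*Combined protocol and SAP*

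**What the plan says.** The Design section describes the main study as an observational matched design and states what controls confounding: "Since randomization is not possible in this study, we will rely on inclusion criteria and matching to reduce the potential for confounding". The factors are given as "matched on age, race, education, and smoking rate". Target Population says "Participants in the HIV+ and HIV- groups will be matched according to key demographic and smoking characteristics (see Accrual below"), but the Accrual section does not describe matching. The plan therefore does not say whether matching is by individual pairs or by group, or with what tolerance.

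Under Data Analysis, Aim 1 is a linear regression on the abstinence-induced change, and Aim 2 is an ordinary logistic regression: "The hypothesized effect of HIV status (HIV+ vs. HIV-) will be tested by including a dichotomous term using the *z*-score". On covariates, Aim 1 says "Although the groups will be matched on key variables, we may also include a small number of covariates (e.g., nicotine dependence, Shipley IQ"), with entry at p=0.1. Aim 2 likewise tests a small number of other variables at p=0.1. A preliminary step compares characteristics with HIV status and with outcomes, and puts forward for entry those that show potential to predict outcome (p=0.2). No factor is forced in, and no matched-set, conditional or clustered analysis is named.

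The primary set is everyone who went through the laboratory phase and began nicotine replacement. Incomplete smoking data after that point count as smoking.

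**The concern.** HIV status is not randomised, so matching carries much of the protection against confounding in all three aims. The Aim 1 wording treats matching as a reason for adjustment to be optional. Matching balances only the people who were matched, and several protocol steps can remove people before nicotine replacement starts: the carbon monoxide criterion at the abstinent session, repeat drug screens at the laboratory visits, and blood pressure. If such losses depend on smoking rate or age and differ by HIV group, the analysed groups are no longer balanced on the design factors.

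The groups may also start far apart. Target Population gives 78% African American for the HIV clinical core, against 16% and 52% racial/ethnic minorities in two earlier trials at the centre. The patch regimen is set by cigarettes per day, so an imbalance in smoking rate is also an imbalance in treatment. Aim 3 proceeds only if Aim 2 shows an HIV effect, so a confounded Aim 2 result would pass into the mediation claim.

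**Working it through.** **1. Does the sizing allow for matching?** Inputs from Power Analysis and Sample Size: 150 per group; Aim 1 d=0.4 at alpha 0.01; Aim 2 60/45, 50/35 and 40/25 at alpha 0.05 (two-sided assumed, as sidedness is not stated).

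- Aim 1, independent samples: d√(n/2) − z = 0.4×√75 − 2.576 = 0.888, power 81.3%. The stated 80% reproduces.
- Aim 2, z-test on log-odds, 50 v 35: log OR = 0.619; SE = √(1/(150×0.25) + 1/(150×0.2275)) = 0.2366; 0.619/0.2366 − 1.96 = 0.66, power 74.4%. For 60 v 45 it is 73.6%, and for 40 v 25 it is 78.7%. Only the last is within 2 points of 80%.

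These figures are consistent with formulas that took no account of matching. The Aim 2 shortfall is a separate matter.

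**2. What brings a matching factor into the model?** Association with outcome at p=0.2, then p=0.1. The preliminary step looks at association with HIV status, but nothing follows from it. The named examples (gender, nicotine dependence, depression, nicotine metabolite ratio, Shipley IQ) include none of the four factors. The lists are open, however, so the factors are eligible.

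**3. If balance is lost, what does omission cost?** The documents give no prognostic strength or imbalance, so both are assumed: a combined slope of 0.5–0.75 log-odds per SD and a residual imbalance of 0.2–0.3 SD, with no true HIV effect. Simulated type I error, 150 v 150, four factors, 3,000 runs per setting:

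| Model | Type I error |
|---|---|
| HIV term only | 6.2–13.1% |
| p=0.2 screen, then p=0.1 entry, applied to the four factors | 4.5–5.8% |
| Four factors forced in | 4.2–5.2% |

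Monte Carlo error near 5% is √(0.05×0.95/3000) = 0.4 points. With one combined score, a 35% quit rate and 1,500 runs, the HIV-only model showed a spurious difference of 2.4–4.4 points.

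**4. How plausible is that imbalance?** 300/415 = 72.3% retained, a 27.7% loss over the whole study. If the HIV+ group alone lost 27.7% before treatment, a 0.3 SD shift needs a dropout slope of about 1.5 log-odds per SD; a slope of 0.5 gives 0.13 SD. At 10% loss and slope 0.5, the shift is 0.05 SD. Modelling attrition directly (207 enrolled pairs, about 27% lost before treatment, dependent on the score in HIV+ only) gave an odds-ratio bias of 1.04–1.14 and type I error of 4.4–6.6% unadjusted, against about 5% with the score fitted.

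**5. If matching is individual and ignored.** With v = p1q1 + p0q0, the matched variance is vt = v − 2ρ√(p1q1·p0q0). For 50 v 35, v = 0.25 + 0.2275 = 0.4775. At ρ=0.10, vt = 0.4775 − 0.0477 = 0.4298 and √(vt/v) = 0.949. The actual size of the nominal 5% test is 2(1 − Φ(1.96/0.949)) = 3.9%. ρ is assumed throughout.

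| ρ | True SE / reported SE | Actual size | Power, matching ignored | Power, matching used |
|---|---|---|---|---|
| 0 | 1.000 | 5.0% | 75.8% | 75.8% |
| 0.05 | 0.975 | 4.4% | 76.3% | 77.9% |
| 0.10 | 0.949 | 3.9% | 76.9% | 80.0% |
| 0.20 | 0.895 | 2.8% | 78.3% | 84.4% |

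Slopes of 0.5, 0.75 and 1.0 per SD correspond to within-pair correlations of about 0.05, 0.11 and 0.17. Fitting the score in a logistic model then gives power of 77.2% v 76.8%, 79.9% v 77.4% and 81.3% v 76.8%, fitted v not fitted.

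**The case against.** The strongest reply is that the plan already has a route for these factors. Intake collects smoking history and demographics as possible covariates, the screening lists are open, and a factor strong enough to confound is usually strong enough to be admitted. The simulation bears this out: with the screening applied to the four factors, size stays near nominal. This stands, and it limits the point to a missing guarantee.

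Three stronger readings are tempting, and the documents do not support them.

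- *The models exclude the matching factors, so the plan runs at 6–13% false positives.* That range belongs to a model with no covariates. The plan's selection rules allow the factors in.
- *The error bars are wrong.* This requires close or individual matching on prognostic factors. The plan speaks of matched groups and does not describe pairs. Where it applies, the error makes the test conservative and is small at low correlation. Aim 1 analyses a within-subject change, for which correlation between matched subjects may be smaller still.
- *Attrition of about 28% destroys the match.* The 415-to-300 figure covers withdrawal through follow-up. For Aim 2 only losses before nicotine replacement remove anyone, and how many those are is not stated. Enrolment also continues until 150 per group complete, so balance might be maintained as recruitment proceeds; the plan does not say.

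**Conclusion.** The point holds in a limited form. The plan names four factors as its protection against confounding and then leaves their place in the primary models to an optional p-value screen that responds to prediction of outcome and not to imbalance by HIV status. The exposure is bias if a factor is omitted and pre-treatment losses differ by HIV group in relation to it. Under the assumed slopes and imbalances, type I error is about 6–13% with no covariates, about 5–6% with the screening applied to these factors, and about 5% with them forced in. The upper part of the first range needs strong, one-sided loss. The direction of any bias depends on who is lost.

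The precision issue is secondary: standard errors about 3–5% too large at an assumed within-match correlation of 0.05–0.10, and only if matching is close or individual. The confounding issue does not depend on pairs, because fitting the four factors is the remedy under group matching too. No effect on Aim 3 has been quantified.

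**What to change.** In Data Analysis, replace the optional wording with a fixed rule: the Aim 1 and Aim 2 models always contain age, race, education and baseline cigarettes per day, whatever their p-values, and any screened covariates are added to these. Carry the same four into the Aim 3 equations. State the matching method (individual or group, and the tolerances) in Accrual, where Target Population already sends the reader. If matched sets are formed, cluster standard errors on set; conditional logistic regression would discard subjects whose match was lost. Report the balance of the four factors by HIV group in the analysis set, and give the marginal (standardised) quit-rate difference beside the adjusted odds ratio.

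The cost is a few lines of text and roughly 4–6 degrees of freedom out of 300. The adjusted odds ratio becomes conditional on the factors, which the marginal difference offsets. No new data should be needed: age, education and smoking rate are listed among the Intake measures, and race, though not named in that list, must be recorded for the matching to be done.

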**Aim 3.** Assuming that we find a significant effect of HIV+ status on abstinence at EOT, we will use a correlational and regression-based path model approach for examining mediation of HIV status effects (MacKinnon et al., 2007). Candidate mediators include five cognitive performance task measures (Neurocognitive Outcomes and Table 1), and will be represented as pre-post differences, continuously distributed and treated as normal. The effects of HIV status on candidate mediators, and of mediators on outcome will be assessed using a generalized path model (Stata GSEM), with the model reporting standardized coefficients. The path model partitions the effect of group on outcome into direct (and unexplained) effects versus mediated effects. We will then test the overall mediation hypothesis using the proportion of group effect explained [87, 88, 90] and the strength of each mediating pathway as follows. We will estimate the model for HIV status predicting abstinence without mediators, to estimate the direct effect of status in the unadjusted model ( $\hat{\beta}^*$ ). We will then test whether HIV status predicts the candidate mediators, and in turn, test whether mediators predict abstinence in an adjusted group effect model, and estimate the effect of HIV status in the mediator adjusted model ( $\beta^*$ ). Finally, we will calculate the proportion of HIV status effect explained, which is calculated as  $1 - (\hat{\beta}^* / \hat{\beta}^*)$ ; the standard error for this quantity is calculated using the delta method, and the mediation hypothesis will be tested using a *z*-test. The

primary analysis tested at  $\alpha=0.05$  will be global mediation – when all candidate mediators are included in the model, a significant proportion of the HIV status effect will be explained. We will also conduct a secondary analysis using products of the coefficients along each mediating path using a delta-method based z-test.

Exploratory Aim. Using the path model described above we will quantify the proportion of variance explained by each cognitive domain (e.g., executive function, verbal memory, and response inhibition) in the relationship between HIV status and abstinence rates. Since this test is exploratory, we do not have specific hypotheses about which domain will account for more variance and these analyses will be used for hypothesis generating for future work.

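### Aim 3's primary test, a z-test on the proportion of the HIV effect explained, has much lower power than the total indirect effect and often misses mediation that the latter detects

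*Combined protocol and SAP*

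**What the plan says.** Under Statistical Analysis, Data Analysis, Aim 3 starts with a condition: "Assuming that we find a significant effect of HIV+ status on abstinence at EOT". The model for HIV status without mediators is fitted "to estimate the direct effect of status in the unadjusted model"; despite that label, this coefficient is the total HIV effect, the one tested in Aim 2. A second model adds the mediators. The proportion explained is one minus the ratio of adjusted to unadjusted coefficient; "the standard error for this quantity is calculated using the delta method, and the mediation hypothesis will be tested using a" z-test.

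The test at the 5% level "will be global mediation – when all candidate mediators are included in the model". On the mediators: "Candidate mediators include five cognitive performance task measures". On the outcome model, Aim 2 states: "We will analyze point-prevalence quit rates using logistic regression". Both coefficients are therefore log odds ratios.

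The power section names the same target: "The primary aim will be to test the overall fraction of the effect mediated". It claims 80% power at d = 0.32.

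Products of coefficients appear only as follows: "We will also conduct a secondary analysis using products of the coefficients along each mediating path using a delta-method based z-test". No test of their sum, the total indirect effect, is named. Nor does the plan say how the covariance between the two separately fitted HIV coefficients enters the delta method.

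**The concern.** Three features of the statistic work against it.

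- Its denominator is the Aim 2 estimate, which the design makes only just large enough to detect.
- Its two coefficients come from logistic models with different covariates. Odds ratios are non-collapsible: adding predictors of abstinence moves the HIV coefficient away from zero even without mediation. This offsets part of the shrinkage that the ratio is meant to measure.
- The natural alternative, the summed indirect effect, is left untested.

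Aim 3 carries the trial's mechanistic conclusion. A non-significant primary test could be reported as evidence that cognition does not mediate, while the indirect effect in the same data is significant. Changing the statistic after such a result would look post hoc.

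**Working it through.** **Inputs from the documents.** 150 v 150; abstinence 60/45, 50/35 or 40/25%; five mediators entered together; alpha 0.05; Aim 2 must be significant; missing abstinence counted as smoking, so no subjects are lost.

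**Assumed, because the documents do not give them.** Shift of each mediator between HIV groups 0.32 to 0.4 SD; correlation between mediators 0 to 0.3; true share mediated 30 to 100% on the log-odds scale of the full model; two-sided testing; joint covariance of the two coefficients included in the delta method.

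**1. The plan's own figure.** For two means with 150 per group and d = 0.32, z = 0.32 x sqrt(150/2) = 2.77. Two-sided power is Phi(2.77 - 1.96) = 79.1%, and exactly 80% needs d = 0.323. The stated 80% is thus what a two-sided comparison of two means gives. The document does not name the procedure used, but this is not a calculation for a ratio of coefficients.

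**2. The denominator.** Expected z = log odds ratio / sqrt[1/(150 p1 q1) + 1/(150 p2 q2)], with q = 1 - p:

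- 40 v 25%: 0.693 / sqrt(1/36 + 1/28.125) = 0.693 / 0.252 = 2.75; power about 79%
- 50 v 35%: 0.619 / 0.237 = 2.62; power about 74%
- 60 v 45%: 0.606 / 0.234 = 2.59; power about 74%

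**3. Why the ratio test is weak.** Let c and c' be the unadjusted and adjusted coefficients, V and V' their variances, C their covariance, r = c'/c. The delta method gives SE(1 - r) = sqrt(V' + r^2 V - 2rC) / |c|, so

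z = |c - c'| / sqrt(V' + r^2 V - 2rC).

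Let k = SE(c')/SE(c). In logistic regression adjustment does not reduce the standard error, so k is at least 1. The covariance is at most SE(c) x SE(c'). For r between 0 and 1, z is then at most z(Aim 2) x (1 - r)/(k - r), hence at most z(Aim 2). The ratio test inherits the strength of Aim 2 as a ceiling, however clear the indirect effect. In the simulations it was essentially never significant unless Aim 2 was.

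**4. Simulated power at 40 v 25%, given a significant Aim 2.** Ranges run over the shifts and correlations above. The last two columns multiply by the 79% chance of passing Aim 2.

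| True share mediated | Ratio test | Total indirect effect | Ratio, overall | Indirect, overall |
|---|---|---|---|---|
| 30% | 13-25% | 39-73% | 10-20% | 31-58% |
| 50% | 46-58% | 84-97% | 36-46% | 66-77% |
| 80-100% | 37-90% | about 100% | 29-71% | about 79% |

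A separate simulation at shift 0.32 (6,000 trials per scenario) gives 19-22% v 51-70% at 30% mediated and 44-57% v 93-97% at 50%. At 80% it gives 44-84%, and at 100% it gives 35-87%, both against about 100%. Median z at half mediation is 1.9-2.0 for the ratio and 3.0-3.1 for the indirect effect.

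**5. How often the ratio test misses.** Among trials in that second simulation with both Aim 2 and the indirect effect significant, the ratio test fails in 62-69% (30% mediated), 39-54% (50%), 16-55% (80%) and 13-65% (100%).

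**6. Scale.** The median estimated proportion is about 0.36 to 0.43 when the true value is 0.5. A ratio formed inside one path model, indirect / (indirect + direct), misses only 5-16% at half mediation and under 1% at 80%. Much of the loss therefore comes from using two separate models.

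**7. If the covariance is left out.** With C = 0, V' = V and r = 0.5, z = 0.5 x 2.75 / sqrt(1.25) = 1.23, well short of 1.96. The simulated miss rates become about 100% (30% mediated), 98-99% (50%), 67-78% (80%) and 29-61% (100%).

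**The case against.** **The Aim 2 condition protects the ratio.** Aim 3 runs only after a significant HIV effect, which removes denominators near zero. This stands, and the power comparison above is conditional on it. The losses remain after conditioning. The condition also limits what any replacement can gain, because overall success cannot exceed about 79%.

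**The test does not usually fail.** A reader might infer that it misses real mediation more often than not. As a general statement the evidence does not support that. With the covariance included, misses exceed one half at about 30% mediation, with weak mediator shifts (at 0.2 SD and correlation 0.3, power is 5% v 78% at half mediation), and in some strongly mediated cases with correlated mediators. Around half mediation they lie near one half, and with strong mediation and uncorrelated mediators they are well below it.

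**The inputs are assumed.** Shift, correlation and share mediated are not in the documents, and sidedness is not stated. One-sided, the ratio test reaches 88% at half mediation with shift 0.4 and correlation 0.3. The plan's own power figure, however, matches a two-sided test: one-sided, d = 0.32 would give Phi(2.77 - 1.645) = 87%, not 80%. The numbered sources cited for the method could not be consulted.

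**The error is on the safe side, and path products are planned.** Both are true. With no mediator effect the ratio test rejected in 0.3% of simulated trials, and the indirect effect in about 2%. A reader might infer a risk of false claims; there is none here. But five single-path tests do not answer the global question, and at half mediation with five active mediators only about half of the trials passing Aim 2 had any significant path.

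**Conclusion.** The point holds as a loss of power. The primary Aim 3 statistic is tied to the strength of Aim 2 and compares coefficients on different scales. Under the stated assumptions the total indirect effect had higher power in every scenario run. At half mediation, overall success is about 36-46% for the planned test, against 66-77% for the indirect effect. The sizes depend on the assumed mediator inputs; the direction does not change across the range examined.

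The noisy denominator is not the whole cause, since the difference in scale between the two logistic models matters as well.

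Severity is should-fix. The declared primary outcomes are cognitive performance and end-of-treatment abstinence, the sample size was set mainly by Aim 2, and the consequence is a missed mechanistic finding. If the covariance were omitted from the delta method the position would be considerably worse, but the plan's silence does not show that it would be.

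**What to change.** In the Aim 3 analysis text and in Power Analysis and Sample Size:

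- Make the primary global test the total indirect effect from the single GSEM already planned: the sum over the five mediators of (HIV to mediator) x (mediator to abstinence). Test it with a two-sided 95% percentile-bootstrap interval, resampling subjects within HIV group. In a small check of 150 simulated trials, without the Aim 2 condition, this interval gave 93% power at half mediation with shift 0.4, and 3% rejection with no mediator effect.
- Report the proportion explained descriptively, formed inside the same path model as indirect / (indirect + direct), with a bootstrap interval.
- Replace the Aim 3 power statement with a simulated figure for the new test, stating the mediator assumptions and the Aim 2 condition.

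The cost is SAP wording, one bootstrap run and a short simulation; no new data are needed. The proportion explained loses its own p-value. The change should be made before the outcome data are analysed.

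### The secondary path-by-path mediation test in Aim 3 is conservative and can miss pathways whose two links are both significant; a bootstrap, Monte Carlo or joint-significance rule would recover power at almost no cost

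*Combined protocol and SAP*

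**What the plan says.** Aim 3 is analysed only if Aim 2 finds a significant effect of HIV status on end-of-treatment abstinence. A path model is then fitted with five cognitive measures as candidate mediators. The primary Aim 3 test is global: the proportion of the HIV effect explained with all mediators in the model, tested at 5%.

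For the separate paths, the Data Analysis section (Aim 3) specifies a "secondary analysis using products of the coefficients along each mediating path using a delta-method based z-test". It names no bootstrap, distribution-of-the-product or joint-significance method. The same paragraph also tests each link by itself (HIV status on each mediator, each mediator on abstinence), but gives no rule for combining the two results into a conclusion about mediation.

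The nearest stated error level is in Power Analysis and Sample Size, where "the component individual deficits will be treated as secondary and tested individually as part of an exploratory analysis, also with a 5% type 1 error". No power is given for the path tests and no effect size for the mediator-to-abstinence link. That section says only that "we will test whether abstinence-induced cognitive deficits predict quit rates".

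**The concern.** For one cognitive measure, no mediation means a·b = 0: a is zero, b is zero, or both are. The planned test divides the estimated product by its delta-method standard error and reads the result as a standard normal z. That reference fits poorly when either path is zero or modest, and the misfit always makes rejection harder.

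What is at stake is which cognitive measures are reported as carrying the association between HIV status and relapse. A pathway can have both links significant in the same data and still be declared non-significant. The plan sized Aim 3 for small-to-medium effects, which is the region where this happens most.

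**Working it through.** **Inputs.** Group sizes are from Power Analysis and Sample Size ("With 150 HIV+ vs. 150 HIV- smokers"). Alpha is 5%; sidedness is not stated, and two-sided is assumed because it reproduces the plan's figures. For the a path, the plan's figure for HIV status on each abstinence-induced deficit is Aim 1's d = 0.4. Aim 3's d = 0.32 belongs to the global test and is used here only as a lower value. The b path is not in the documents; an expected z of 2 to 3.5 is assumed for the main range, with stronger values shown. The estimates of a and b are taken as independent.

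**Step 1: the plan's own figures.** With 150 per group and unit SD, the expected z is d·√(150/2) = d·√75.
- Aim 3: 0.32·√75 = 2.77. Power at 5% is Φ(2.77 − 1.96) = 79.1%, against a stated 80%.
- Aim 1: 0.4·√75 = 3.46. Power at 1% is Φ(3.46 − 2.576) = 81.3%, against a stated 80%.

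Both reproduce.

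**Step 2: the statistic.** The delta-method standard error of a·b is √(a²·SE_b² + b²·SE_a²). Dividing the numerator and denominator of the test by SE_a·SE_b gives

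z = z_a·z_b / √(z_a² + z_b²), or 1/z² = 1/z_a² + 1/z_b².

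So |z| is below both |z_a| and |z_b|, and the test cannot reject unless both links are significant. With equal paths, each must reach 1.96·√2 = 2.77 (p about 0.006).

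**Step 3: rejection under no mediation** (2,000,000 draws per row; one path zero).

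| Expected z of the other path | Planned test | Both paths significant |
|---|---|---|
| 0 | 0.01% | 0.25% |
| 2.8 (about d = 0.32) | 1.0% | 4.0% |
| 3.46 (d = 0.4) | 1.6% | 4.7% |
| 5 | 3.1% | 5.0% |
| 10 | 4.6% | 5.0% |

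The first row can be checked by hand. With both paths zero, the statistic is normal with SD 0.5, so P(|z| > 1.96) = P(|Z| > 3.92), about 0.01%.

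**Step 4: power when both paths are real** (planned test v both paths significant, points lost in brackets).

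| b-path expected z | a path d = 0.32 (z = 2.77) | a path d = 0.4 (z = 3.46) |
|---|---|---|
| 2 | 19.8% v 40.8% (21) | 29.9% v 48.2% (18) |
| 2.5 | 32.1% v 55.8% (24) | 46.5% v 65.9% (19) |
| 2.8 | 39.8% v 63.2% (23) | 56.2% v 74.6% (18) |
| 3.5 | 56.0% v 74.2% (18) | 74.9% v 87.6% (13) |
| 6 | 75.2% v 79.1% (4) | 91.5% v 93.4% (2) |

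Both paths at z = 4: 91.0% v 95.9% (5 points). Both at z = 5: 99.5% v 99.8% (under 1 point). With d = 0.32 and b at 2.8, the planned test reports no mediation in 1 − 39.8/63.2 = 37% of the datasets where both links are significant.

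**Step 5: check in the trial's own layout.** This used 3,000 simulated trials per setting, 150 v 150, a logistic outcome with roughly 20–30% quitting, and five mediators with correlation 0.3 (assumed), one of them active. The columns are planned test, both paths significant, and Monte Carlo interval for the product.

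| a path, b log-odds per SD (assumed) | Planned | Joint | Monte Carlo |
|---|---|---|---|
| 0, 0 | 0.0% | 0.2% | 0.2% |
| d = 0.32, 0 | 0.9% | 4.2% | 3.2% |
| d = 0.4, 0 | 1.9% | 4.7% | 4.3% |
| d = 0.32, 0.42 | 35.5% | 60.1% | 57.5% |
| d = 0.4, 0.42 | 50.9% | 71.8% | 70.5% |
| d = 0.4, 0.50 | 65.6% | 83.0% | 81.7% |
| d = 0.5, 0.60 | 90.8% | 95.7% | 95.7% |

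These agree with Steps 3 and 4. The alternatives gain power while staying at or below 5%. The simulations do not condition on a significant Aim 2 result. In a one-mediator run at d = 0.32 and log-odds 0.35, conditioning on it changed little: 37% v 61% became 38% v 62%.

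**The case against.** **A conservative test keeps its promise.** Rejecting less than 5% of the time respects a 5% limit, so a reader who infers that the stated type 1 error is breached would be wrong. The alternatives also fall far below 5% when both paths are zero (about 0.2%). This stands. The point is about lost power, not false claims.

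**The size depends on the inputs.** It is tempting to say that the test rejects 0–1% under the null and loses 20–25 points. That describes a paths near d = 0.32 with a moderate b path, close to the worst case. The d = 0.32 figure is attached to the global mediation test, and at Aim 1's d = 0.4 the loss is smaller. When one path is strong the test approaches its nominal level. This stands, so the result has to be given as a range.

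**The link tests are also planned.** A reader might take the product test to be the only analysis that shows which measure carries the association. It is not: both links are tested for each mediator, and a careful reader would see both results. What remains is that the plan gives no rule for combining them, and the only formal test of a path is the product z-test.

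**The scope is narrow.** The analysis is secondary and follows a significant Aim 2 result. Nor should the point be extended to the Exploratory Aim. That text says "Using the path model described above we will quantify the proportion of variance explained by each cognitive domain" and states no product z-test.

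**Conclusion.** The point holds as a refinement worth considering for a secondary analysis. The path-specific test is conservative by construction. Under no mediation it rejects about 0.01% with both paths zero and about 1–2% with one path at d = 0.32–0.4, nearing 5% only with a very strong path. Against joint significance it loses about 13 to 24 points of power for a paths of d = 0.32–0.4, if the b path has an expected z of about 2 to 3.5. That b-path range is an assumption, as the documents give no value. If both paths are strong, the loss is minor.

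The algebra in Step 2 needs no assumption about effect sizes; only the size of the loss does. The calculation says nothing about the primary proportion-explained test, which is a different statistic.

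**What to change.** In Data Analysis, Aim 3, replace the delta-method z-test for the path products with one of the following, chosen before analysis:

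- a 95% percentile bootstrap interval for each product, resampling subjects within HIV group, or a 95% Monte Carlo interval for the product, with mediation along a path concluded if the interval excludes zero; or
- a rule that both path coefficients must be significant at 5%.

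This takes one sentence of plan text and a few lines of code on the same fitted path model. It needs no new data or participants. The price is a little computing time and, for the interval methods, intervals that are not symmetric around the estimate.
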